8.3 Safety and toxicity reporting requirements

The Safety and Toxicity Reporting Committee (STRC) is responsible for reviewing SAEs for WFBCCC Institutional studies as outlined in Appendix C. STRC currently requires that all unexpected 4 and all grade 5 SAEs on these trials be reported to the STRC for review. Any grade 3 to 5 product infusion reactions must also be reported. All WFBCCC Clinical Research Management (CRM) staff members assisting a Principal Investigator in investigating, documenting and reporting an SAE that qualifies for STRC reporting are responsible for informing a clinical member of the STRC – as well as the entire committee – via the email notification procedure of the occurrence of an SAE.

8.4 WFUHS IRB AE reporting requirements

Any unanticipated problems involving risks to subjects or others and adverse events shall be promptly reported to the IRB, according to institutional policy. Reporting to the IRB is

Safety and Immunologic Activity of Multiple Infusions of APN401

Wake Forest Baptist Comprehensive Cancer Center

CCCWU 03716

required regardless of the funding source, study sponsor, or whether the event involves an investigational or marketed drug, biologic or device. Reportable events are not limited to physical injury, but include psychological, economic and social harm. Reportable events may arise as a result of drugs, biological agents, devices, procedures or other interventions, or as a result of questionnaires, surveys, observations or other interactions with research subjects.

All members of the research team are responsible for the appropriate reporting to the IRB and other applicable parties of unanticipated problems involving risk to subjects or others. The Principal Investigator, however, is ultimately responsible for ensuring the prompt reporting of unanticipated problems involving risk to subjects or others to the IRB. The Principal Investigator is also responsible for ensuring that all reported unanticipated risks to subjects and others which they receive are reviewed to determine whether the report represents a change in the risks and/or benefits to study participants, and whether any changes in the informed consent, protocol or other study-related documents are required.

Any unanticipated problems involving risks to subjects or others occurring at a site where the study has been approved by the WFUHS IRB (internal events) must be reported to the WFUHS IRB within seven calendar days of the investigator or other members of the study team becoming aware of the event.

Any unanticipated problems involving risks to subjects or others occurring at another site conducting the same study that has been approved by the WFUHS IRB (external events) must be reported to the WFUHS IRB within seven calendar days of the investigator or other members of the study team becoming aware of the event.

Any event, incident, experience, or outcome that alters the risk versus potential benefit of the research and as a result warrants a substantive change in the research protocol or informed consent process/document in order to insure the safety, rights or welfare of research subjects.

8.5 FDA reporting requirements

IND sponsors are responsible for compliance with the Federal Food, Drug, and Cosmetic Act and the implementing regulations (Title 21 of the Code of Federal Regulations). Those responsibilities include: (1) reporting any unexpected fatal or life threatening adverse experience associated with use of the drug by telephone or fax no later than 7 calendar days after initial receipt of the information [21 CFR 312.32(c)(2)]; (2) reporting any adverse experience associated with use of the drug that is both serious and unexpected in writing no later than 15 calendar days after initial receipt of the information [21 CFR 312.32(c)(1)]; and (3) submitting annual progress reports (21 CFR 312.33).

8.5.1 Sterility failure, result of investigation of the cause and any corrective actions, must be reported in an information amendment submitted to the FDA in a timely manner, within 30 calendar days after initial receipt of the positive culture test (21 CFR 312.31). If the patient experiences any serious and unexpected adverse experience that could be from administration of the sterility failure of the cellular product, then this information must be reported to the FDA in an IND safety report no more than 15 calendar days after the initial receipt of the information (21 CFR 312.32).

Safety and Immunologic Activity of Multiple Infusions of APN401
Wake Forest Baptist Comprehensive Cancer Center
CCCWU 03716

8.5.2 If study stopping rules are met and if it is determined that the investigational drug presents an unreasonable and significant risk to subjects, all investigations are to be discontinued and the FDA, all Institutional Review Boards, and all investigators need to be notified (21 CFR 312.56(d)).

9.0 Clinical Response

9.1 Definitions

Response and progression will be evaluated in this study using the new international criteria proposed by the Response Evaluation Criteria in Solid Tumors (RECIST) Committee [JNCI 92(3):205-216, 2000]. Changes in only the largest diameter (unidimensional measurement) of the tumor lesions are used in the RECIST criteria. Note: lesions are either measurable or non-measurable using the criteria provided below. The term “evaluable” in reference to measurability will not be used because it does not provide additional meaning or accuracy.

9.1.1 **Measurable disease:** Measurable lesions are defined as those that can be accurately measured in at least one dimension (longest diameter to be recorded) as ≥ 20 mm with conventional techniques (PET, CT, MRI, x-ray) or as ≥ 10 mm with spiral CT scan. All tumor measurements must be recorded in millimeters (or decimal fractions of centimeters).

9.1.2 **Non-measurable disease:** All other lesions (or sites of disease), including small lesions (longest diameter <20 mm with conventional techniques or <10 mm using spiral CT scan), are considered non-measurable disease. Bone lesions, leptomeningeal disease, ascites, pleural/pericardial effusions, lymphangitis cutis/pulmonis, inflammatory breast disease, abdominal masses (not followed by CT or MRI), and cystic lesions are all non-measurable.

9.1.3 **Target lesions:** All measurable lesions up to a maximum of five lesions per organ and 10 lesions in total representative of all involved organs should be identified as target lesions and recorded and measured at baseline. Target lesions should be selected on the basis of their size (lesions with the longest diameter) and their suitability for accurate repeated measurements (either by imaging techniques or clinically). A sum of the longest diameter (LD) for all target lesions will be calculated and reported as the baseline sum LD. The baseline sum LD will be used as reference by which to characterize the objective tumor response.

9.1.4 **Non-target lesions:** All other lesions (or sites of disease) should be identified as non-target lesions and should also be recorded at baseline. Non-target lesions include measurable lesions that exceed the maximum numbers per organ or total of all involved organs as well as non-measurable lesions. Measurements of these lesions are not required but the presence or absence of each should be noted throughout follow-up.

Safety and Immunologic Activity of Multiple Infusions of APN401

Wake Forest Baptist Comprehensive Cancer Center

CCCWU 03716

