3.0 Selection of Patients

3.1 Inclusion criteria

- 3.1.1 Patients with histologically confirmed inoperable, recurrent or metastatic malignant solid tumors, deemed incurable, and who have either:
 - failed to respond to standard therapy or
 - for whom no standard therapy is available or
 - refuse to receive standard therapies

The study is intended to enroll patients with pancreatic and colorectal cancer. Patients with other types of solid tumors will require approval by the Principal Investigator.

- 3.1.2 Measurable disease as defined by RECIST (see Section 9.0)
- 3.1.3 Patients with treated, stable, and asymptomatic brain metastases are eligible
- 3.1.4 Patients on every 2, 3 or 4 week systemic therapy programs must be off the treatment program for at least 2, 3, or 4 weeks, respectively, and must have recovered from any clinically significant toxicity experienced. Patients on weekly or daily systemic therapy programs and patients receiving radiation must be at least 1 week since treatment and recovered from any clinically significant toxicity experienced. Must be at least 4 weeks and have recovered from major surgery

Safety and Immunologic Activity of Multiple Infusions of APN401

Wake Forest Baptist Comprehensive Cancer Center

CCCWU 03716

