Appendix E – RECIST Measurement Form

TUMOR RESPONSE WORKSHEET (Modified RECIST)					CCCFU # _____			
Patient Name: _____					Patient MRN: _____			
Has patient had localized RT @ baseline?  No  Yes If yes, which lesions? : _____								
Target Lesions								
TARGET Lesions	Lesion	Site	Imaging (ie, CT, MRI)	Baseline Date: (Se, Im)	Cycle_____ Date: (Se, Im)	Cycle_____ Date: (Se, Im)	Cycle_____ Date: (Se, Im)	Cycle_____ Date: (Se, Im)
	01			mm	mm	mm	mm	mm
	02			mm	mm	mm	mm	mm
	03			mm	mm	mm	mm	mm
	04			mm	mm	mm	mm	mm
	05			mm	mm	mm	mm	mm
		Sum of Diameters		mm	mm	mm	mm	mm
NON-TARGET Lesions	% Change (% Δ) from Baseline or Nadir* & absolute value (AbV)		NA	% Δ	NA	AbV	NA	AbV
	Target Lesion Response		N/A					
Non-Target Lesions								
NON-TARGET Lesions	Lesion	Site	Imaging	Baseline	Cycle_____ _____	Cycle_____ _____	Cycle_____ _____	Cycle_____ _____
	01							
	02							
	03							
	04							
	05							
		Non-Target Lesion Response		N/A				

Safety and Immunologic Activity of Multiple Infusions of APN401
 Wake Forest Baptist Comprehensive Cancer Center
 CCCWFU 03716

New Lesions							
New	1			N/A			
	2			N/A			
	3			N/A			
Overall Tumor Response				Cycle ____	Cycle ____	Cycle ____	Cycle ____
Radiologist Signature/Date:							
Treating Physician Signature/Date:							
PI Signature:							

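### Previously irradiated lesions enter the target set without restriction, so shrinkage from recent radiotherapy can contribute to a response or stable disease that the trial would credit to APN401

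*Combined protocol and SAP*

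**What the plan says.** **Measurable (9.1.1, 9.1.2).** "Measurable lesions are defined as those that can be accurately measured in at least one dimension", subject to a minimum diameter that depends on the imaging technique. The list of non-measurable disease does not mention irradiated lesions.

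**Target (9.1.3).** The target set is "All measurable lesions up to a maximum of five lesions per organ and 10 lesions in total". On selection: "Target lesions should be selected on the basis of their size (lesions with the longest diameter) and their suitability for accurate repeated measurements".

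**Non-target (9.1.4).** This class holds whatever is left: "Non-target lesions include measurable lesions that exceed the maximum numbers per organ or total of all involved organs as well as non-measurable lesions". Irradiated lesions are not named.

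**Entry.** Section 3.1.2 requires "Measurable disease as defined by RECIST (see Section 9.0"). Section 3.1.4 and the Appendix A checklist state that "patients receiving radiation must be at least 1 week since treatment and recovered from any clinically significant toxicity experienced". The synopsis asks for at least 4 weeks since radiation.

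**Timing of scans.** Baseline imaging may be up to 4 weeks before treatment (Sections 6.0 and 9.2). The first response scan is at Day 71.

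**Form.** Appendix E asks "Has patient had localized RT @ baseline" and, if so, which lesions. Nothing in Sections 9.1 to 9.4, Section 11.4.3 or Appendix F refers to that answer.

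**The concern.** A lesion irradiated shortly before entry may still be shrinking from the radiotherapy after the baseline measurement. As written, the plan puts that lesion in the baseline sum and judges the patient by the change in the sum. There is no control arm, so nothing in the data tells a radiotherapy effect from an APN401 effect.

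PR, SD and the timing of PD are at stake, and PD feeds PFS. Section 1.4 shows how small counts get read in this programme: it reports three patients with stable disease after a single infusion and links them to immune responses. One misattributed PR or SD here could be read in the same way.

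**Working it through.** The plan states no response rate, power or sample size for response, so there is no figure of its own to reproduce. The check has four parts.

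**1. Is there any rule that keeps an irradiated lesion out?** Measurability in 9.1.1 turns on diameter and technique, and the exclusions in 9.1.2 do not cover radiotherapy. Below the caps, 9.1.3 takes every measurable lesion. Above them, it chooses by size and repeatability. Section 9.1.4 lists only over-cap and non-measurable lesions. So no stated rule moves an irradiated measurable lesion to non-target status, and the Appendix E answer has no use.

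**2. Timing.**
- Under 3.1.4 and Appendix A radiotherapy may end 7 days before entry, and the baseline scan may be 28 days old. The scan can then predate the end of radiotherapy by up to 28 − 7 = 21 days.
- Under the synopsis interval, with both counted to the same date, the difference is 28 − 28 = 0. This particular route closes, but the lesion is still a target.
- SD needs one qualifying assessment at least eight weeks (56 days) after entry (9.4.1). The Day 71 scan alone can meet that.
- PR needs a repeat assessment four weeks later. That shows the shrinkage lasted, not what caused it.

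**3. Shrinkage needed for PR.** PR is a fall of at least 30% in the target sum from baseline (9.3.1). Let w be the irradiated lesion's share of the baseline sum and s its shrinkage, with all other lesions unchanged. The sum falls by w × s, so PR requires s ≥ 0.30 / w. The shares are assumed, because the documents give none.

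| Share w | Shrinkage needed, 0.30 / w |
|---|---|
| 100% | 30% |
| 75% | 40% |
| 60% | 50% |
| 50% | 60% |
| 40% | 75% |
| 30% | 100% |
| 25% | 120%, impossible |

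Below a 30% share the lesion cannot produce PR alone, though it can still contribute.

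Delay of PD, again with assumed sizes: take two 40 mm targets, sum 80 mm. The irradiated one falls 60% to 16 mm and the other grows to 50 mm.
- Sum: 16 + 50 = 66 mm, and 66/80 − 1 = −17.5%, which is SD.
- The untreated lesion alone: 50/40 − 1 = +25%, which would be PD.
- PD is then judged from the 66 mm nadir: 66 × 1.20 = 79.2 mm. With the irradiated lesion still at 16 mm, the other must reach 63.2 mm, and 63.2/40 − 1 = +58%. A new lesion or non-target progression would trigger PD sooner.

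**4. Effect of one patient on the response rate.** The plan speaks of six plus four patients and also of 12, so both totals are shown, with exact (Clopper-Pearson) 95% intervals.
- n = 12: from 0/12 (0 to 26.5%) to 1/12 = 8.3% (0.2 to 38.5%).
- n = 10: from 0/10 (0 to 30.8%) to 1/10 = 10% (0.3 to 44.5%).

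**The case against.** The strongest reply is that little depends on this. Response is a secondary outcome summarised as counts and percentages, and the survival plots are exploratory (11.4.3). Expansion and stopping depend on toxicity, and immunologic activity on interferon production or the neutrophil to lymphocyte ratio (11.4.2). With at most 12 patients and the Appendix E field, a response in an irradiated lesion could be footnoted. This stands as a limit on impact. It does not supply a rule, and one chosen after the scans are known would be hard to defend.

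A second reply is that Section 9.1 cites published RECIST criteria, which might deal with irradiated lesions. That source is not part of the documents and cannot be judged here. The protocol writes out its own definitions, and those are silent.

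A reader might go further and infer that irradiated lesions must be targets and that their shrinkage will count as response. The text does not go that far. Section 9.1.3 uses should, applies caps and allows for suitability for repeat measurement. PR needs a confirmed fall of at least 30% in the whole sum.

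A reader might also infer that a patient whose only measurable lesion was irradiated cannot show drug activity and ought to be ineligible. Nothing in the documents supports the first half, and the second is a separate question in a trial whose primary aim is toxicity.

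**Conclusion.** The gap is real and its reach is limited. The stated target rule places irradiated lesions in the sum and gives no route out, while the information needed to handle them is already collected. Radiotherapy shrinkage can contribute to PR or SD and delay PD. It can produce PR alone only when the lesion is at least 30% of the baseline sum and shrinks by 0.30 divided by its share. One such patient moves the response rate by 8.3 or 10 points.

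These sizes rest on assumed lesion shares and shrinkage. The documents do not say how many patients will have had recent radiotherapy, nor how such lesions behave over time, so no expected bias can be given. Overall survival, the toxicity rules and the immune endpoints are unaffected.

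It would be wrong to treat entry one week after radiotherapy as settled. Section 3.1.4 and Appendix A contradict the synopsis on this and the passages must be reconciled. The target-lesion gap exists under either interval.

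**What to change.** Add a rule to 9.1.3 and 9.1.4: a lesion flagged in Appendix E as previously irradiated is followed as non-target unless progression in that lesion was documented after the radiotherapy. Refer to the rule in Appendix F. At minimum, prespecify in 11.4.3 that response and PFS are also reported with flagged lesions left out of the sum.

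Placing the rule in 9.1.3 and 9.1.4, and not in 9.1.1, leaves the definition of measurable disease alone, so eligibility under 3.1.2 does not change.

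The cost is a couple of sentences, since the form already has the field. Some patients will have fewer target lesions, and a patient whose only measurable lesion was irradiated would not be evaluable for target response. The alternative of a second summary avoids changing the main classification, but leaves the main figures open to the same question.

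Separately, reconcile the radiation interval between the synopsis, Section 3.1.4 and Appendix A.

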9.2 Measurable disease guidelines

All measurements should be taken and recorded in metric notation using a ruler or calipers. All baseline evaluations should be performed as closely as possible to the beginning of treatment and never more than four weeks before the beginning of the treatment.

- The same method of assessment and the same technique should be used to characterize each identified and reported lesion at baseline and during follow-up. Imaging-based evaluation is preferred to evaluation by clinical examination when both methods have been used to assess the antitumor effect of a treatment.
- Clinical lesions. Clinical lesions will only be considered measurable when they are superficial (e.g., skin nodules and palpable lymph nodes). In the case of skin lesions, documentation by color photography, including a ruler to estimate the size of the lesion, is recommended.
- Chest X-ray. Lesions on chest x-ray are acceptable as measurable lesions when they are clearly defined and surrounded by aerated lung. However, CT is preferable.
- Conventional CT and MRI. These techniques should be performed with cuts of 10 mm or less in slice thickness contiguously. Spiral CT should be performed using a 5 mm contiguous reconstruction algorithm. This applies to tumors of the chest, abdomen, and pelvis. Head and neck tumors and those of extremities usually require specific protocols.
- PET-CT. At present, the low dose or attenuation correction CT portion of a combined PET-CT is not always of optimal diagnostic CT quality for use with RECIST measurements. However, if the site can document that the CT performed as part of a PET-CT is of identical diagnostic quality to a diagnostic CT (with IV and oral contrast), then the CT portion of the PET-CT can be used for RECIST measurements and can be used interchangeable with conventional CT in accurately measuring cancer lesion over time. Note, however, that the PET portion of the CT introduces additional data which may bias an investigator if it is not routinely or serially performed.
- Ultrasound (US). When the primary endpoint of the study is objective response evaluation, US should not be used to measure tumor lesions. It is, however, a possible alternative to clinical measurements of superficial palpable lymph nodes, subcutaneous lesions, and thyroid nodules. US might also be useful to confirm the complete disappearance of superficial lesions usually assessed by clinical examination.
- Endoscopy, laparoscopy. The utilization of these techniques for objective tumor evaluation has not yet been fully and widely validated. Their uses in this specific context require sophisticated equipment and a high level of expertise that may only be available in some centers. Therefore, the utilization of such techniques for objective tumor response should be restricted to validation purposes in reference centers. However, such techniques can be useful to confirm complete pathological response when biopsies are obtained.

Safety and Immunologic Activity of Multiple Infusions of APN401

Wake Forest Baptist Comprehensive Cancer Center

CCCFU 03716

- Tumor markers. Tumor markers alone cannot be used to assess response. If markers are initially above the upper normal limit, they must normalize for a patient to be considered in complete clinical response.
- Cytology, histology. These techniques can be used to differentiate between partial responses (PR) and complete responses (CR) in rare cases (e.g., residual lesions in tumor types such as germ cell tumors, where known residual benign tumors can remain).

9.3 Response criteria

9.3.1 Evaluation of target lesions

- Complete Response (CR): Disappearance of all target lesions
- Partial Response (PR): At least a 30% decrease in the sum of the longest diameter (LD) of target lesions, taking as reference the baseline sum LD
- Progressive Disease (PD): At least a 20% increase in the sum of the LD of target lesions, taking as reference the smallest sum LD recorded since the treatment started or the appearance of one or more new lesions
- Stable Disease (SD): Neither sufficient shrinkage to qualify for PR nor sufficient increase to qualify for PD, taking as reference the smallest sum LD since the treatment started

9.3.2 Evaluation of non-target lesions

- Complete Response (CR): Disappearance of all non-target lesions and normalization of tumor marker level
- Incomplete Response/Stable Disease (SD): Persistence of one or more non-target lesion(s) or/and maintenance of tumor marker level above the normal limits
- Progressive Disease (PD): Appearance of one or more new lesions and/or unequivocal progression of existing non-target lesions
- Although a clear progression of “non-target” lesions only is exceptional, in such circumstances, the opinion of the treating physician should prevail, and the progression status should be confirmed at a later time by the review panel (or study chair).

9.3.3 Evaluation of best overall response

The best overall response is the best response recorded from the start of the treatment until disease progression/recurrence (taking as reference for progressive disease the smallest measurements recorded since the treatment started). The patient's best response assignment will depend on the achievement of both measurement and confirmation criteria (see section 9.4.1).

Safety and Immunologic Activity of Multiple Infusions of APN401
 Wake Forest Baptist Comprehensive Cancer Center
 CCCWFU 03716

Target Lesions	Non-target Lesions	New Lesions	Overall Response
CR	CR	No	CR
CR	Incomplete response/SD	No	PR
PR	Non-PD	No	PR
SD	Non-PD	No	SD
PD	Any	Yes or No	PD
Any	PD	Yes or No	PD
Any	Any	Yes	PD

Note: Patients with a global deterioration of health status requiring discontinuation of treatment without objective evidence of disease progression at that time should be classified as having “symptomatic deterioration.” Every effort should be made to document the objective progression, even after discontinuation of treatment. In some circumstances, it may be difficult to distinguish residual disease from normal tissue. When the evaluation of complete response depends on this determination, it is recommended that the residual lesion be investigated (fine needle aspirate/biopsy) before confirming the complete response status.

